Eltrombopag for post transplant thrombocytopenia
2009-0106

Core Protocol Information

Study Chairman:	[name]
Department:	Stem Cell Transplantation and Cellular Therapy
[contact]
Unit:	423
Full Title:	Eltrombopag for post transplant thrombocytopenia
Protocol Phase:	Phase II
Version Status:	Terminated 04/16/2018
Version:	20
Document Status:	Final

Abstract

Objectives:

Primary Objective

- 1.1 To compare the efficacy of eltrombopag and placebo as defined by proportion of patients achieving platelet count $\geq 30 \times 10^9/l$ by day 57 in patients with thrombocytopenia post hematopoietic cell transplantation (HCT).

Secondary Objectives

- 1.2 To describe and estimate toxicity graded as per National Cancer Institute (NCI) criteria.
- 1.3 To estimate clinical benefit as defined by:
 - 1.3.1 Proportion of patients achieving platelet count $\geq 50 \times 10^9/l$ by day 57
 - 1.3.2 Number of platelet and red cell transfusions
 - 1.3.3 Bleeding as determined by NCI criteria
- 1.4 To determine the optimum dose of eltrombopag in this patient population.
- 1.5 To estimate pre and post treatment thrombopoietin levels and correlate these with platelet response.
- 1.6 To measure drug level and correlate it with response.

Rationale: (Be as concise as possible)

Low platelet count, which is usual after HCT, significantly increases the risk of bleeding. The incidence of bleeding post HCT is 34%, which is moderate or severe in 23% of the patients. Currently regular platelet transfusion remains the mainstay of therapy, with most patients requiring platelet transfusion several times a week. This imposes a significant burden on transfusion services and increases the cost.

Reduced platelet production is a major cause of thrombocytopenia post transplant with increased platelet destruction playing a minor role. Platelet recovery occurs between 11 – 28 days post transplant. Delayed platelet recovery (primary thrombocytopenia) occurs in 5%-25% of patients 8 weeks after HCT. Furthermore, 20% of patients develop secondary thrombocytopenia, defined as a drop in platelet count not due to disease relapse after an initial platelet recovery. Secondary thrombocytopenia is caused by both impaired production and increased destruction resulting from dysregulated immune system. It is often associated with Graft versus host disease and drugs like ganciclovir.

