Thrombopoietin (TPO) is the primary regulator of platelet production, and is required for proliferation and differentiation of its precursors. Eltrombopag is a nonpeptide small molecule that stimulates thrombopoiesis by activating TPO receptor.

Eltrombopag received approval from the FDA for the treatment of chronic Idiopathic Thrombocytopenic Purpura (ITP). In a randomized placebo controlled trial in patients with ITP, 59% eltrombopag patients and 16% placebo patients responded achieving a platelet count $\geq 50,000$ per μL with an odds ratio of 9.61 (95% CI 3.31-27.86; $p < 0.0001$). It also increases platelet counts in patients with thrombocytopenia and cirrhosis due to hepatitis C.

In light of its significant efficacy in increasing platelet production and modest toxicity, It is certainly a promising agent for patients who develop thrombocytopenia post stem cell transplantation.

Eligibility: (List All Criteria)

Inclusion:

- 1) Patients ≥ 35 days post HCT with Platelet count $\leq 20 \times 10^9/\text{l}$ sustained for 7 days or patients are platelet transfusion dependent, and
- 2) Neutrophil count $\geq 1.5 \times 10^9/\text{l}$ anytime within the last seven days before enrollment. Patients can be on myeloid or erythroid growth factors for example filgrastim), and
- 3) Age ≥ 18

Exclusion:

- 1) Recurrence or progression of primary malignancy after HCT
- 2) ALT ≥ 2.5 times the ULN

- 3) Serum bilirubin >2mg/dl (unless due to Gilbert's syndrome)
- 4) Documented deep vein thrombosis within 1 year before enrollment on the study, except if upper arm thrombosis related to central venous catheters, within 3 months before enrollment on the study.
- 5) ECOG Performance status >2
- 6) Pregnancy: Women of child-bearing potential and men must agree to use contraception prior to study entry and for the duration of study participation. A woman of child-bearing potential is defined as a woman who has not been naturally post-menopausal for at least 12 consecutive months or with no previous surgical sterilization. A negative pregnancy test result will be required before any study drug is given.

Is there an age limit? Yes

Why? Provide scientific justification:

It is a new molecule that has not been previously tested in children.

Disease Group:

Blood And Marrow Transplantation

Treatment Agents/Devices/Interventions:

Eltrombopag

Proposed Treatment/Study Plan:

Dosage and Administration

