5.2 Evaluations During Study

Table 3 Monitoring

	Pre Study (within 3 days of consent)	Week 1-12 (every 2 wks)###	Post Completion of study drug**
CBC, Na, K, Cl, CO ₂ , ALT, Bili, Alk Phos, albumin, tot protein, BUN & creatinine	X	X	X
PT/PTT	X		X
Thrombopoietin	X		X
PK Studies		X^^	
Toxicity assessment (history and PE) (Graded per NCI toxicity criteria)	X	X	X
Bone Marrow (incl reticulin and collagen staining)	X#		X^
B-HCG pregnancy test in women of child- bearing age	X##		
No. of Platelet & RBC transfusions	X (in the 4 wks prior to study entry)	X	X
Immune Reconstitucional Studies ***	X		X
Ophthalmic Evaluation	X ⁺		X ⁺⁺

A previous biopsy done within one year is acceptable for baseline purposes and a separate bone marrow biopsy will not be required. To assess for fibrosis, special staining for reticulin and collagen will be performed.

Negative pregnancy test is required prior to receiving drug but is not required prior to consent.

Visits at Week 10 and 12 will done by telephone interview and blood work can be drawn locally.

^ First routine bone marrow done after study completion for assessment of disease status will be stained for reticulin and collagen to assess fibrosis. The bone marrow will be performed within 3 months after the last dose of study drug.

^^ No PK studies will be drawn for weeks 10 and 12.

** Date of last dose of study drug.

+ Within 6 months of study entry.

** Within 3 months of last dose of study drug. This will be done earlier if patients develop visual symptoms indicative of cataract.

*** Peripheral blood T-cell subsets, NK and B-cell immune reconstitution

Note: All assessments to be done within 3 days of stated time point.

Statistical Considerations:

Overview

This will be a randomized, double-blind Phase II trial to compare eltrombopag and placebo in patients with thrombocytopenia post transplant. The primary endpoint will be development of a platelet count $\geq 30 \times 10^9/l$ by day 57 without platelet transfusion.

Adaptive Randomization

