We will use a Bayesian adaptive algorithm (Berry, 1994) to randomize patients between the two treatment arms. The first 20 patients will be randomized fairly (i.e. fixed allocation of 1:1) between the two arms, after which the response adaptive randomization will begin. As the trial progresses and data accrue, the randomization will become unbalanced in favor of the treatment that, on average, has better results in terms of response, so that each successive patient is more likely to receive the treatment showing better results.

The randomization algorithm based upon this method will be implemented by using the Clinical Trial Conduct website developed by the Department of Biostatistics at M.D. Anderson Cancer Center.

The target enrollment for the study is a maximum of 64 patients, and we expect to enroll an average of 2 patients per month. We will follow all patients until they go off study. We assume a Beta(0.4, 1.6) prior distribution for the probability of response in each arm. We use the following notation: We denote the response rate in the placebo arm as R_p , and the response rate in the eltrombopag arm as R_E . We then denote P_p as the probability that the response rate in the placebo arm is greater than the response rate in the eltrombopag arm. Formally,

$$P_p = \text{Prob}(R_p > R_E \mid \text{data from patients evaluated at day 57}) \text{ and} \\ P_E = 1 - P_p = \text{Prob}(R_E > R_p \mid \text{data from patients evaluated at day 57})$$

The trial will be stopped early and eltrombopag (placebo) selected as being superior if at any time during the course of the trial $P_p > 0.98$ (< 0.02). If the trial is not stopped early and all 64 patients are enrolled and evaluated at day 57, then eltrombopag will be declared superior (inferior) if $P_p > 0.975$ (< 0.025).

After the first 20 patients are randomized fairly, patients will be randomized to the eltrombopag arm with probability $\max(0.20, P_p)$ and to the placebo arm with probability $\max(0.20, P_e)$. In other words, randomization probabilities are subject to the constraint that the minimum randomization probability to either arm is 20%.

The primary endpoint is development of a platelet count $\geq 30 \times 10^9/l$ at day 57 without platelet transfusion within 7 days. Patients who drop out of the trial before completion of day 57 with a platelet count $\geq 30 \times 10^9/l$ at the time of discontinuation will be considered successes with respect to the primary endpoint.

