Patients who drop out of the study after being randomized but before receiving any study drug will not be included in the analysis and will be replaced. All patients who receive a single dose of study drug will be included in the analysis.

Safety Monitoring

Patient safety will be monitored during this trial by reviewing the rate of development of toxicity, relapse, and mortality.

If a patient develops a grade 3 or higher toxicity attributed to the drug, the study drug will be stopped in that patient. This may be recommenced at the discretion of PI after resolution of the toxicity and review of the data.

For grade 4 toxicity, the PI will routinely review patient data and will temporarily halt the study pending study team review if a high rate of unexpected grade 4 toxicity is noticed. The case report form used for data collection will be PDMS/CORE.

We will use a formal Bayesian monitoring rule to monitor the rate of death or relapse on this study. We wish to ensure that the rate of death/relapse at day 57 is no more than 30% in either study arm. If there is a high probability that this rate is greater than 30% in either arm, we will temporarily halt and review the data with the MDACC IRB and FDA before continuing.

The method of Thall, Simon, and Estey will be employed separately in each arm to perform this monitoring. We will assume a noninformative Beta(0.6, 1.4) distribution on the prior probability that a patient experiences death or relapse, which has a mean of 30% but carries little prior information. We will start monitoring with the first patient in each arm and will use the following rule: halt accrual onto an arm if at any time during the course of the study:

$$\Pr\{57\text{-day death/relapse on the arm} > 30\% \mid \text{data from patients evaluable at day 57}\} > 0.925$$

In other words, if at any time during the trial, we determine that there is greater than a 92.5% chance that the 57-day death/relapse in an arm is greater than 30%, we will temporarily halt the arm pending IRB and FDA review.

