This rule leads to the following stopping boundaries: halt the trial if the number of patients that have died/relapsed in an arm out of the number of patients evaluable at day 57 in that arm is $\geq 2/2, 3/3, 4/5, 5/7, 6/8, 7/12, 8/14, 9/17, 10/20, 11/22, 12/25, 13/28, 14/31, 15/33, 16/36, \text{ and } 17/39$. If a decision to stop depends upon data from patients that have been enrolled but who have not yet reached day 57, accrual will temporarily be halted until enough patients are evaluable as to be able to reach this decision. Anticipated study enrollment is 1-2 patients per week, but as an additional safety measure, first 4 patients will be enrolled at a minimum interval of two weeks between consecutive patients.

Joint Operating Characteristics of Adaptive Randomization and Safety Rules
(See table in protocol.)

Analysis Methods
(Details in protocol.)

Where Will Participants Be Enrolled:

Only at MDACC

Is this an NCI-Cancer Therapy Evaluation Protocol (CTEP)? No

Is this an NCI-Division of Cancer Prevention Protocol (DCP)? No

Estimated Accrual:

Total Accrual at MDACC: 64
Estimated monthly accrual at MDACC: 2

Accrual Comments:

Do you expect your target population to include non-english speaking participants? Yes

Please select expected languages of non-English speaking participants. (Select all that apply)
Expected languages of non-English speaking participants:

Spanish

Location of Treatment:

This protocol is performed on an Outpatient basis.

Length of Stay: What is the length & frequency of hospitalization?

N/A

Return Visits: How often must participants come to MDACC?

Every 2 weeks for first eight weeks during the period of active treatment

Home Care: Specify what, if any, treatment may be given at home.

1) Observation without any treatment from week 9 to 12 and 2) Open label phase after week 12 if patient chooses to enrol in it.

Name of Person at MDACC Responsible for Data Management: [[name]](#)

Prior protocol at M. D. Anderson:

Has the Principal Investigator ever had a clinical or behavioral protocol at MDACC that accrued patients?
Yes

Data Monitoring Committee:

Is treatment assignment randomized? Yes

Is this a blinded or double-blinded study? Yes

Does this Protocol need data safety monitoring? Yes

Provide the name of the data safety monitoring board (DSMB) monitoring this protocol:
MDACC DMC

Does this protocol have a schedule for interim and final analysis? Yes

Please describe:
Bayesian adaptive design

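### The rule for patients who drop out before day 57 scores success on platelet count alone and omits the 7-day transfusion-free condition applied at day 57

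*Combined protocol and SAP*

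**What the plan says.** Under Statistical Considerations, Adaptive Randomization, the primary endpoint is a platelet count of at least 30 × 10⁹/l "at day 57 without platelet transfusion within 7 days". The sentence that follows deals with early leavers: "Patients who drop out of the trial before completion of day 57 with a platelet count" of at least 30 × 10⁹/l "at the time of discontinuation will be considered successes with respect to the primary endpoint". It sets no transfusion condition. It also does not say how other leavers are scored; failure is only implied.

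The endpoint is worded differently elsewhere. The Overview has "by day 57 without platelet transfusion", with no window. Primary Objective 1.1 begins "To compare the efficacy of eltrombopag and placebo as defined by proportion of patients achieving platelet count", then names the threshold and day 57, and does not mention transfusion.

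Three other statements bear on the point:

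- Inclusion criterion 1 admits patients with a sustained low count, and also those where "patients are platelet transfusion dependent".
- On the analysis set: "All patients who receive a single dose of study drug will be included in the analysis". Only patients who leave before any dose are excluded and replaced.
- Analysis Methods refers the reader to a fuller text ("Details in protocol") that is not part of the supplied document.

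**The concern.** The 7-day condition is there so that a count raised by a recent transfusion is not credited to the study drug. Completers are held to it. As written, leavers are not, so a leaver can meet a looser definition of response than a completer. In a trial that admits transfusion-dependent patients, a count of 30 × 10⁹/l or more at exit can simply reflect a recent transfusion.

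The same response outcome sets the allocation probabilities after the first 20 patients, drives early stopping and decides the final comparison. An error in scoring therefore enters all three. With at most 64 patients, a few such cases could matter.

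**Working it through.** **1. The definitions side by side**

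| Place | Count (× 10⁹/l) | When | Transfusion condition |
|---|---|---|---|
| Objective 1.1 | ≥ 30 | by day 57 | none |
| Overview | ≥ 30 | by day 57 | no transfusion, window not given |
| Adaptive Randomization, endpoint | ≥ 30 | at day 57 | none within 7 days |
| Adaptive Randomization, dropouts | ≥ 30 | at discontinuation | not stated |

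Take a dosed patient with a count of 30 or more who was transfused in the previous 7 days. At day 57 that patient is a failure. At an earlier exit, by the last row, the same patient is a success.

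**2. Inputs**

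The supplied text gives no assumed response rates, power, dropout rate or transfusion rate, so there is no stated figure to reproduce. The calculations below only show scale.

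- From the document: Beta(0.4, 1.6) prior in each arm; first 20 patients allocated 1:1; minimum allocation 20%; maximum 64 patients; limits 0.98 (early) and 0.975 (final); 2 patients per month.
- Assumed: 32 per arm in step 3; true response rates of 20% v 20% and 40% v 20% (eltrombopag v placebo) in step 4; the share k of non-responders mis-scored.
- Convention: P_E = Prob(R_E > R_p), with eltrombopag superior when P_E exceeds the limit. The labelling of P_p in that section is a separate point.

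**3. One patient near the final cut-off**

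With x responders among n, the posterior is Beta(0.4 + x, 1.6 + n − x).

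- 12/32 v 5/32: Beta(12.4, 21.6) v Beta(5.4, 28.6), P_E = 0.977. This is above 0.975 and below 0.98.
- One placebo dropout mis-scored, 12/32 v 6/32: Beta(12.4, 21.6) v Beta(6.4, 27.6), P_E = 0.953. Superiority is lost.

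Any cut-off behaves this way, and the situation is uncommon. Among simulated trials that reach 64 patients, one extra eltrombopag success turns non-selection into selection in 1.0% (20% v 20%) and 6.6% (40% v 20%).

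**4. Equal mis-scoring in both arms**

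If a share k of true non-responders is scored as success, the observed rate is p + (1 − p)k. The observed difference is then (p_E − p_P)(1 − k): for k = 5%, 20 × 0.95 = 19 points; for k = 10%, 20 × 0.90 = 18 points. The arm with more non-responders gains more false successes.

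Simulation: 400,000 trials per case; allocation to eltrombopag equal to P_E limited to 0.20–0.80 after the first 20; outcomes lagging 4 patients (2 per month over 57 days); a look after each evaluated patient; safety rule not applied. The Monte Carlo standard error is about 0.05 points near 12% and 0.08 near 50%.

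| k | Observed rates, null | Eltrombopag selected | Observed rates, true 40% v 20% | Eltrombopag selected |
|---|---|---|---|---|
| 0 | 20 v 20% | 12.2% | 40 v 20% | 56.9% |
| 1% | 20.8 v 20.8% | 12.3% | 40.6 v 20.8% | 56.0% |
| 2% | 21.6 v 21.6% | 12.4% | 41.2 v 21.6% | 55.1% |
| 5% | 24 v 24% | 12.5% | 43 v 24% | 52.7% |
| 10% | 28 v 28% | 12.7% | 46 v 28% | 48.9% |

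For scale, k = 1% corresponds to 10% of non-responders dropping out with 10% of those mis-scored (0.10 × 0.10). k = 5% corresponds to 20% dropping out with 25% mis-scored (0.20 × 0.25).

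Starting looks only after 20 evaluated patients gives the same pattern. At the null, selection is 9.8% (k = 0) and 9.5% (k = 5%). At 40% v 20% it is 53.3, 51.3, 48.7 and 44.6% for k = 0, 2, 5 and 10%. The null level of about 10–12% comes from the simulated design and its look schedule, not from the dropout rule.

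**5. Mis-scoring in one arm only**

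Nothing in the document supports this case. If the observed eltrombopag rate alone rose by 1 or 5 points at the null, false selection would be 13.7% or 20.5%.

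**The case against.** The strongest reply is that the sentence was never meant to loosen the endpoint. It follows directly on the definition with the 7-day window and speaks of success on that same endpoint, so it can be read as moving only the time of assessment. The supplied text also defers its analysis methods to a fuller protocol, where the condition may be stated.

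Few patients are exposed. Each must be dosed, leave before day 57, have a count of at least 30 × 10⁹/l and have been transfused in the previous 7 days. Section 5.1.5 lists patient request as the only early reason for coming off study, apart from the high-count rule in 5.1.2. Blinding makes similar mis-scoring in the two arms the reasonable default, and a 1% share costs about 1 point of power.

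The cut-off example also concerns a rare path. In a shorter simulation of 20,000 trials per case, about 98% of eltrombopag selections came before all 64 patients were evaluated (0.117 of 0.119 at 20% v 20%; 0.558 of 0.570 at 40% v 20%).

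Most of this stands as a limit on size. The effect may be small, the cut-off example shows sensitivity rather than likelihood, and the one-arm shifts carry no weight as evidence. It does not remove the defect. Three wordings of the endpoint leave the carry-over reading unconfirmed, and two careful readers could score the same patient differently. If the fuller protocol has the condition, this sentence should repeat it.

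**Conclusion.** The point holds. Followed as written, the dropout rule counts a transfusion-supported platelet count as a primary response, which the day-57 definition excludes. The case rests on a primary-endpoint rule with more than one reading, not on a demonstrated large bias.

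Under the assumed rates and equal mis-scoring, the type I side is essentially unaffected. The loss in the chance of selecting a truly better eltrombopag is 0.9 points at k = 1% (56.9 − 56.0), 4.2 at 5% (56.9 − 52.7) and 8.0 at 10% (56.9 − 48.9). Which of these is realistic cannot be known from the document, and neither can the direction if the arms differ. The wording should be corrected. Confidence is medium, because the intent and the fuller protocol are not visible.

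**What to change.** Reword the dropout sentence so that a patient who leaves before day 57 is a success only if the count at discontinuation is at least 30 × 10⁹/l with no platelet transfusion in the previous 7 days. State that any other dropout who received study drug is a failure. Use the same transfusion wording in Objective 1.1 and the Overview.

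If the fuller protocol has none, add one sensitivity analysis that scores all dropouts before day 57 as failures. Patients taken off under 5.1.2 keep that section's scoring in both analyses. The conflict between 5.1.2 and 5.1.4/5.1.5 on follow-up is separate, and those sections must be reconciled.

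The cost is one clause and one extra analysis. Table 3 lists numbers of transfusions rather than dates, but the 7-day window cannot be applied to completers without dates; the same dates are needed for leavers. The downside is that a true responder transfused in the week before leaving counts as a failure, so the reported response rate may be slightly lower.

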5.1 Monitoring and Dose adjustment

5.1.1 Patients in the treatment group will be started at dose level 0 (table 1), the dose will be modified every 2 weeks based on the schema outlined in table 2 after a careful review of safety information at the previous dose level.

Table 1 Dose Level

Dose level	Eltrombopag dose

-1	25mg
0	50mg
1	75mg
2	125mg
3	150mg

Table 2 Dose Modification Schema

Platelet count X 10 ⁹ /l	Dose
< 50	Increase by 1 dose level
50-200	No change
201-400	Decrease by 1 dose level
> 400 at any time	Stop the drug

- 5.1.2 Drug will be stopped and patients will be taken off study if at any time platelet count is $\geq 400 \times 10^9/l$. This count will be carried forward to day 57 for analysis of primary endpoint and counted as success.
- 5.1.3 Patients of East Asian ancestry will start at dose level -1 and dose escalation will stop at dose level 2 (maximum dose 125 mgs).
- 5.1.4 The study drug will be stopped after 8 weeks and all patients will be monitored for additional 4 weeks after the last dose of study drug.
- 5.1.5 Patients will be taken off study: 1) at patient request, or 2) after completing 12 weeks.

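### Two rules score patients who leave before day 57 as primary-endpoint successes, and neither says what happens if the patient dies before day 57

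*Combined protocol and SAP*

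**What the plan says.** The last paragraph of Adaptive Randomization (Statistical Considerations) defines the primary endpoint as a count of at least 30 × 10⁹/l "at day 57 without platelet transfusion within 7 days".

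Two rules then give a score to patients who leave before that day:

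- **Drop-out rule** (same paragraph). "Patients who drop out of the trial before completion of day 57 with a platelet count" of at least 30 × 10⁹/l "at the time of discontinuation will be considered successes with respect to the primary endpoint".
- **Carry-forward rule** (section 5.1.2). "Drug will be stopped and patients will be taken off study if at any time platelet count is" at least 400 × 10⁹/l. "This count will be carried forward to day 57 for analysis of primary endpoint and counted as success".

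The paragraph before Safety Monitoring fixes the analysis set: "All patients who receive a single dose of study drug will be included in the analysis". Section 5.1.5 gives the remaining off-study reasons: "Patients will be taken off study: 1) at patient request, or 2) after completing 12 weeks". Death and relapse are not among them.

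Safety Monitoring treats death or relapse by day 57 as an endpoint of its own: "We wish to ensure that the rate of death/relapse at day 57 is no more than 30% in either study arm". Nothing there links that event to the efficacy score.

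**The concern.** Every dosed patient is analysed, so a dosed patient who dies before day 57 needs a primary-endpoint score. The two early-leaver rules look only at the platelet count and ignore what happens between leaving and day 57. A response rate defined at day 57 can then include patients who were not alive at day 57.

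This score is used three times: in the randomization probabilities after the first 20 patients, in the early-stopping rule, and in the final superiority call. If such cases fell mostly in one arm, that arm would look better than it was, later patients would be steered towards it, and a declaration of superiority would be hard to interpret. The problem is separate from whether the transfusion condition applies to drop-outs, because it arises even when the exit count was free of transfusion.

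**Working it through.** **Reading the rules against the possible cases**

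| Patient | Applicable text | Score as written |
|---|---|---|
| Drops out with count ≥30, dies before day 57 | Drop-out rule | Success |
| Taken off study with count ≥400, dies before day 57 | Section 5.1.2 | Success |
| Dies on study before day 57, last count ≥30 | None, unless death is a drop-out | Not stated; can be read as success |
| Relapses and drops out before day 57 with count ≥30 | Drop-out rule | Success |
| Relapses, stays on study | Endpoint definition | Actual day-57 count |

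The first two rows need no interpretation. In the third row the supplied text leaves three options open. The patient is a success if death counts as dropping out. The patient is a failure if the endpoint needs a count at day 57. Or the patient is left out of the running posterior, because that posterior is conditioned on patients evaluated at day 57.

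**Is one patient's score enough to matter?**

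The documents give no count of such patients, so there is no figure of the plan's own to reproduce. The following only illustrates sensitivity.

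Inputs from Adaptive Randomization: a Beta(0.4, 1.6) prior in each arm, at most 64 patients, and a final cut-off of 0.975. Assumptions: an even split of 32 and 32, the responder numbers shown, and the cut-off applied to Prob(R_E > R_p). The printed decision rule uses P_p, which is defined in the other direction; that is a separate matter.

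With x successes among n patients, each arm's posterior is Beta(0.4 + x, 1.6 + n − x). Then Prob(R_E > R_p) = ∫ f_E(t) F_p(t) dt over 0 to 1, where f_E is the eltrombopag posterior density and F_p the placebo posterior distribution function.

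| Eltrombopag v placebo successes (32 each) | Prob(R_E > R_p) | Above 0.975? |
|---|---|---|
| 12 v 5 | 0.977 | yes |
| 11 v 5 (one eltrombopag success rescored) | 0.959 | no |
| 10 v 5 (two rescored) | 0.931 | no |
| 11 v 4 (one rescored in each arm) | 0.982 | yes |
| 10 v 3 (two rescored in each arm) | 0.987 | yes |
| 13 v 5 (one more eltrombopag success to begin with) | 0.9875 | yes; falls only to 0.977 if one is rescored |

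Uneven splits behave alike. With 42 and 22 patients and 4 placebo successes, going from 18 to 17 eltrombopag successes moves the posterior from 0.981 to 0.972. With 51 and 13 patients and 3 placebo successes, going from 26 to 25 moves it from 0.977 to 0.969.

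In these examples a superiority call is lost only when the rescored patients are on eltrombopag without a matching number on placebo, and only near the cut-off. Equal rescoring raises the posterior, and it could gain a call: 13 v 6 is 0.973, and one fewer in each arm is 12 v 5, at 0.977.

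For allocation, suppose all of the first 20 patients have been evaluated, 10 per arm. Then 4 v 2 gives 0.83, which the 20% floor for placebo holds to 0.80, and 3 v 2 gives 0.69.

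**The case against.** Four arguments on the other side deserve weight.

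*Death is not called a drop-out.* A reader might infer that the plan enters every death with a last count of at least 30 as a response. The text does not go that far: it speaks of dropping out and of discontinuation, and uses death as a separate term. For deaths on study the scoring is unstated, not stated wrongly. This stands. It does not help with patients who leave first and die afterwards.

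*Overlap is legitimate.* A reader might also infer that being an efficacy success and a safety event at once is a contradiction. It is not. Platelet response and death/relapse are separate endpoints with separate rules, and a relapsed patient may stay on study and have a genuine day-57 count. This stands too, and it is why relapse belongs in a sensitivity analysis.

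*The objective is worded differently.* Objective 1.1 and the Overview speak of reaching the count by day 57, so a response achieved before death might be thought to count. But the definition given alongside the decision rules is tied to day 57 itself, and section 5.1.2 carries a count forward to that day, so the plan evidently needs a status then.

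*The full rules may be elsewhere.* The supplied text refers to the protocol for analysis methods, so the absence of an exception can be asserted only for what is in view. This stands as a limit. Even so, the endpoint and both early-leaver rules are written out here without an exception.

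**Conclusion.** The point holds in limited form. Two stated rules score a patient as a success at day 57 even if that patient has left and died by then, and the scoring of a death on study is open to more than one reading. Because every dosed patient is analysed and the score feeds allocation, stopping and the final call, this should be settled.

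The number of patients affected is unknown. It is tempting to take the 30% death/relapse limit (0.30 × 32 = 9.6 per arm) and derive one to three affected successes per arm. The documents do not support that: 30% is a safety limit on death and relapse together, not an expected number of deaths, and nothing gives the share with a last count of at least 30. Nor do they support saying that a superiority finding would be overturned. The fall from 0.977 to 0.959 assumes 32 per arm, a result just above the cut-off, and the affected patient on eltrombopag with none on placebo. The figures show that one patient's score can matter near the boundary; they do not predict an effect.

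**What to change.** Add one sentence to the drop-out rule and to section 5.1.2: a patient who dies before day 57 is a non-success for the primary endpoint whatever the last count. State that this applies both in the adaptive algorithm and in the final analysis. Report one sensitivity analysis in which relapse before day 57 is also a non-success. If the full protocol's analysis methods already contain a rule for death, reconcile it with these two places.

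The cost is a sentence in each place and one extra analysis. The death and relapse data are already collected for the safety rule, and no treatment rule changes. The downside is that reported response rates may be slightly lower.
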